8.2. Secondary Effectiveness Analysis

[figure not shown]
The number and proportion of thighs with correct identification of baseline vs. 12-week images of the inner thighs by at least two out of three blinded, independent reviewers and the corresponding two-sided exact 95% CI of the proportion of thighs with correct identification will be summarized.

Participants who have reported 'Very satisfied' or 'Satisfied' on each of the CoolSculpting participant questionnaires (upper arms and inner thighs) for question #1 (overall satisfaction) will be categorized as 'Satisfied.' The numbers and proportions of 'Satisfied' at 12-weeks visit will be summarized and two-sided exact 95% CI of the proportions will be provided for arms and thighs, respectively.

Fat reduction using caliper measurements at 12-weeks compared to baseline for upper arms and inner thighs will be summarized descriptively using the change from baseline to week 12 for arms and thighs,

This document is confidential.

respectively. Also, two-sided 95% CI of the mean change from baseline vs. Week 12 will be provided for arms and thighs, respectively.

This document is confidential.

9. Safety

The population used for safety analyses will be the Safety Population (SAF).

Safety will be assessed on the basis of adverse event (AE) or adverse device event (ADE), and other safety assessments.

The numbers and proportions of participants with TEAEs, Serious TEAEs, ADEs, SADEs, unanticipated ADEs, and unanticipated SADEs will be summarized. The numbers and proportions of participant-reported pain scores (0 to 10 scale) will be summarized.

9.1. Treatment Compliance

The treatment compliance will not be applicable in this study.

9.2. Adverse Events

An AE is any untoward medical occurrence, unintended disease or injury, or untoward clinical signs (including abnormal laboratory findings) in participants, users or other persons, whether or not related to the investigational medical device or the comparator device. This definition includes events related to the procedures involved.

An SAE is defined as an AE that:

- led to death
- led to serious deterioration in the health of the participant, that either resulted in
 - a life-threatening illness or injury; or
 - a permanent impairment of a body structure or a body function, or
 - in-patient or prolonged hospitalization; or
 - medical or surgical intervention to prevent life-threatening illness or injury or permanent impairment to a body structure or a body function; or
 - if a participant becomes pregnant, then spontaneous abortion, fetal distress, fetal death, or a congenital abnormality or birth defect is considered an SAE

AEs will be coded using MedDRA V22.1 or higher.

AEs will be defined as treatment-emergent if they start after the first treatment. AEs with missing or partial dates will be handled according to Section **Error! Reference source not found.** with respect to assigning treatment-emergence. As a conservative approach, AEs are considered treatment-emergent unless there is clear indication that the event occurred before the first treatment in the study. In general, only TEAEs will be included in the summary tables, but all AEs will be included in the listings.

The number of participants and the number of TEAEs will be tabulated by SOC and PT, sorted by the decreasing overall frequency of SOC and then by PT in decreasing frequency within each SOC. For summaries by SOC, PT, and maximum severity, a participant will be counted once at the highest severity level for which the event occurred at the SOC level and the highest severity level for each unique PT within that SOC level. Therefore, participants will only contribute once to each PT and once to each SOC level. Severity will be assessed as mild, moderate, or severe. For summaries by SOC, PT, and maximum

This document is confidential.

relationship (to study device or to study procedure), a participant will be counted once at the highest causality level for which the event occurred at the SOC level, and the highest causality level for each unique PT within that SOC level. Therefore, participants will only contribute once to each PT and once to each SOC level. Causality will be assessed in relation to the study device and the study procedure as not related, unlikely, possible, probable, or causal relationship.

An TEAE will be defined as device-related or procedure-related if it is assessed as unlikely, possible, probable, or causal relationship.

The following tables will be produced:

- An overall summary of the number and percentage of participants reporting TEAEs, device-related TEAEs, procedure-related TEAEs, and SAEs, including the total number of device-related TEAEs, procedure-related TEAEs, and TESAEs by overall.
- TEAEs, overall and by SOC and PT.
- TEAEs by maximum severity, overall and by SOC and PT.
- TESAEs, overall and by SOC and PT.

Listings of all AEs, SAEs, and AEs leading to discontinuation by participant will be presented.

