An ADE is defined in accordance with ISO 14155 as “an adverse event related to the use of an investigational medical device.” This definition includes any AEs resulting from insufficient or inadequate instructions for use, deployment, implantation, installation, or operation, or any malfunction of the investigational medical device as well as any event resulting from use error (per ISO 62366) or from intentional misuse of the investigational medical device.

Device Deficiency or Complaints

A device deficiency is defined in accordance with ISO 14155 as inadequacy of a medical device including issues with respect to its identity, quality, durability, reliability, safety, or performance. Device deficiencies include malfunctions, use errors, and inadequate labelling.

If a device deficiency occurs, the investigator will notify Allergan using the CRF. Device deficiencies shall be documented throughout the study and appropriately managed by Allergan. The Clinical Trial Site will enter all the information regarding device deficiency into the appropriate CRFs. Device deficiencies associated with AEs will also require completion of SAE forms. Allergan shall review all device deficiencies and determine and document in writing whether they could have led to a SADE. These shall be reported to the regulatory authorities and IRBs as required by Federal regulations.

Assessment of Severity

Severity is a clinical determination of the intensity of an AE. The severity assessment for a clinical AE will be assigned a category by the investigator as follows:

Mild	An AE that is easily tolerated by the participant, causes minimal discomfort, may require only minimal treatment and does not interfere with everyday activities.
Moderate	An AE that is sufficiently discomforting to interfere with normal everyday activities; intervention may be needed, but poses no significant or permanent risk of harm.
Severe	An AE that prevents normal everyday activities; treatment or other intervention usually needed.

If there is a change in severity of an AE, it must be recorded as a separate event.

Assessment of Causality

Relationship to a device refers to a determination of the relationship (if any) between an AE and the device. A causal relationship is present if the investigator determines that there is a reasonable possibility that the AE may have been caused by the device.

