An AE could be considered procedure-related when, in the judgment of the investigator, it is reasonable to believe that the event is associated with the procedure, regardless of the relationship to the study device. Procedure-related causes that contribute to the occurrence of the

event can be attributed to other products, surgical techniques, or medications required specifically for the procedure.

Every effort will be made by the investigator to assess the relationship of the AE, if any, to the device and/or study procedure. Causality should be assessed using the categories presented in the following table:

Not related	Clinical event of which the relationship to the device and/or procedure can be excluded, such as if the event has an incompatible time relationship to study procedure and/or use of the device, involves a body part or organ not expected to be affected by the device or procedure, could be explained by underlying disease or other drugs or chemicals or is incontrovertibly not related to the study device, and is not due to use error.
Unlikely	Clinical event whose time relationship to use of the device and/or study procedure makes a causal connection improbable, but that could plausibly be explained by underlying disease or other drugs or chemicals.
Possible	Clinical event with a reasonable time relationship to the use of the device and/or study procedure, but that could also be explained by concurrent disease or other drugs or chemicals. Cases where relatedness cannot be assessed or no information has been obtained should also be classified as possible.
Probable	Clinical event with a reasonable time relationship to the use of the device and/or study procedure, and is unlikely to be attributed to concurrent disease or other drugs or chemicals.
Causal relationship	Clinical event with plausible time relationship to the use of the device and/or study procedure, is a known side effect of the product category the device belongs to or of similar devices and procedures; follows a known response pattern to the medical device; involves a body-site or organ that the device or procedures are applied to and/or influence; harm is due to error in use, and that cannot be explained by concurrent disease or other drugs or chemicals.

Follow-up of Adverse Events

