9.3. Adverse Device Event

An ADE is any AE related to the use of an investigational medical device, including those events resulting from insufficient or inadequate instructions for use, deployment, implantation, installation, or operation, or any malfunction of the investigational medical device. This definition includes any event resulting from use error or from intentional misuse of the investigational medical device.

A serious adverse device event (SADE) is an ADE that resulted in any of the consequences characteristic of an SAE (all device or surgical related).

The number of participants and the number of ADEs will be tabulated by SOC and PT, sorted by decreasing overall frequency of SOC and then by PT within SOC.

The following tables will be produced:

- ADEs, overall and by SOC and PT.
- SADEs , overall and by SOC and PT.
- ADEs with maximum severity , overall and by SOC and PT.

All ADEs will be listed, sorting by participant number, start date (placing missing and partial dates first) and end date, alphabetically by SOC, and then by PT within SOC. ADE duration in days will be calculated as (end date - start date + 1) and included in the data listings.

This document is confidential.

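### SAP 9.2 counts TEAEs rated 'unlikely' as device- or procedure-related, which does not fit the protocol's causality criteria, and gives no reason

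*SAP*

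**What the plan says.** SAP 9.2 has causality assessed separately for the device and for the procedure, "as not related, unlikely, possible, probable, or causal relationship". It then sets the analysis rule: a TEAE counts as device- or procedure-related "if it is assessed as unlikely, possible, probable, or causal relationship". The rule feeds the overall TEAE summary in SAP 9.2, which reports both participants and events. SAP Section 10 repeats that summary by site and by generation.

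Protocol 8.2.1, under its assessment of causality, gives the meaning of the ratings:

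- A causal relationship to the device is present if the investigator finds that "there is a reasonable possibility that the AE may have been caused by the device".
- An event can be considered procedure-related when "it is reasonable to believe that the event is associated with the procedure".
- 'Unlikely' is a "Clinical event whose time relationship to use of the device and/or study procedure makes a causal connection improbable", and one that other disease or exposures could plausibly explain.
- On missing information: "Cases where relatedness cannot be assessed or no information has been obtained should also be classified as possible".

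SAP 9.3 states that "An ADE is any AE related to the use of an investigational medical device", without naming the causality levels that count. ADEs and SADEs are listed as safety endpoints in Protocol 5.2 and SAP 4.3.

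**The concern.** The investigator's rating and the reported category part company. An investigator who follows the protocol and picks 'unlikely' has judged the causal link improbable. The SAP reports that event as related.

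The related-event rate is a main safety result of a single-cohort study that, according to Protocol 4.2, is meant to support a regulatory submission. A reader who sees a device-related percentage will take it as the share of participants with an event the investigator thought the device could reasonably have caused. Under SAP 9.2 it is the share for whom the investigator did not rule the device out.

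The rule may also reach the named safety endpoint. SAP 9.3 builds ADEs and SADEs on the word 'related', and the only definition of that word in terms of causality levels is the one in 9.2.

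**Working it through.** No figure in either document can be reproduced here, because neither gives an expected number of 'unlikely' events. The check compares definitions and then derives the direction of the effect.

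**Step 1: the two documents side by side** (protocol meanings paraphrased from 8.2.1)

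| Level | Protocol meaning | Related under SAP 9.2 | Meets the protocol's criteria |
|---|---|---|---|
| Not related | relationship ruled out | no | no |
| Unlikely | link improbable, other explanation plausible | **yes** | **no** |
| Possible | timing fits, other explanation also open; includes unassessable cases | yes | yes |
| Probable | timing fits, other cause not likely | yes | yes |
| Causal relationship | timing fits, known response, no other explanation | yes | yes |

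The two columns differ only in the 'unlikely' row. The last column is an inference from the protocol's definitions, since the protocol does not print such a list.

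**Step 2: is there a stated reason?** SAP 9.2 calls one rule conservative, but that rule decides whether an event is treatment-emergent. It says nothing about causality. Nor is the inclusive cut needed to protect against uncertain causality: the protocol already sends events that cannot be assessed, or that lack information, to 'possible'. What is left in 'unlikely' is events that were assessed and judged improbable.

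**Step 3: direction.** The set {possible, probable, causal} lies inside {unlikely, possible, probable, causal}. So, for device and procedure separately:

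- Related events under the SAP minus related events under the narrower cut = number of events rated 'unlikely', which is at least 0.
- Participants with a related event under the SAP minus participants under the narrower cut = *m*, the number whose highest rating is 'unlikely', which is at least 0. A participant who also has an event rated 'possible' or above adds nothing to *m*.

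**Step 4: scale.** The rate rises by *m*/*N*. The value of *m* is not in the documents. For *N*, assume that all of the approximately 42 planned participants are treated, since the SAP's Safety population is all treated participants.

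- *m* = 0: 0/42 = 0 points
- *m* = 1: 1/42 = 2.4 points
- *m* = 2: 2/42 = 4.8 points
- *m* = 4: 4/42 = 9.5 points

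These values of *m* are illustrative. With fewer treated, or within one site or generation group, the step per participant is larger because the denominator is smaller.

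**Step 5: can a reader undo the rule?** SAP 9.2 explains how participants would be counted in summaries by maximum relationship, but its list of tables to be produced contains no such summary. From the listed tables, 'unlikely' events cannot be separated from 'possible' ones.

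**The case against.** The best defence is that the SAP had to choose a cut and chose an inclusive one. The protocol's statistical section only says that AEs, SAEs, ADEs and SADEs will be summarised. Its causality table keeps 'not related' for events where a relationship can be excluded, and 'unlikely' falls short of that. Counting everything not excluded is pre-specified and can only over-count. SAP Section 2 makes all analyses descriptive, and the only success threshold in the plan concerns the photographs.

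Much of this stands. A reader might infer that the SAP overrides an explicit protocol rule on which levels count as related; there is no such rule. The mismatch is with the protocol's criteria and its definition of 'unlikely'. A reader might also see an undisclosed change, because SAP Section 12 does not mention the cut. That section lists changes to planned analyses, and the protocol planned no cut, so the omission proves little. Nor does the rule hide harm or drive any decision.

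It can also be said that the investigator's rating survives: causality is recorded for each AE on the CRF and all AEs are listed. Whether the listings display causality cannot be checked, because SAP Section 19 places the shells in a separate document.

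The defence does not supply a reason for the rule. An inclusive convention can be legitimate, but the SAP never says it is using one, and the label 'related' tells the reader something else.

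**Conclusion.** The point holds as a mismatch of definitions. SAP 9.2 reports as related a category that the protocol describes as an improbable causal connection, without a rationale. The related-TEAE counts will be equal to or higher than under the protocol's criteria, and never lower.

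The size is unknown and may be zero. The 2.4 points per participant assumes 42 treated, and counts only participants whose highest rating is 'unlikely'. A reader might infer a substantial inflation, but any specific total needs an assumed number of such participants, and the documents give no basis for one.

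A reader might also infer that the ADE tables will disagree with the device-related TEAE row. That is possible but not established. The natural reading of SAP 9.3 is that it takes its meaning of 'related' from 9.2. The tables would then agree, and the ADE and SADE endpoint would include any 'unlikely' events. The gap is that 9.3 does not say so.

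This is worth correcting before database lock. It is a matter of how safety results are labelled and read, and it does not threaten the study's conclusions.

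**What to change.** Make three changes to the SAP:

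1. In 9.2, define device-related and procedure-related as possible, probable or causal relationship.
2. In 9.3, state that ADEs and SADEs use the same cut for relationship to the device.
3. Add to the 9.2 table list a TEAE summary by maximum relationship, for device and for procedure, showing all five levels. The counting rule for it is already written.

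The third change has to go with the first. Without it, narrowing the cut would take 'unlikely' events out of every listed relatedness summary and show them nowhere else.

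The cost is SAP wording, a programming flag and one extra table. Data collection does not change, because the CRF already records causality. The downside is a less inclusive headline count, which the by-level table offsets: anyone who prefers the wider definition can add the 'unlikely' row back.

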9.3. Adverse Device Event

An ADE is any AE related to the use of an investigational medical device, including those events resulting from insufficient or inadequate instructions for use, deployment, implantation, installation, or operation, or any malfunction of the investigational medical device. This definition includes any event resulting from use error or from intentional misuse of the investigational medical device.

A serious adverse device event (SADE) is an ADE that resulted in any of the consequences characteristic of an SAE (all device or surgical related).

The number of participants and the number of ADEs will be tabulated by SOC and PT, sorted by decreasing overall frequency of SOC and then by PT within SOC.

The following tables will be produced:

- ADEs, overall and by SOC and PT.
- SADEs , overall and by SOC and PT.
- ADEs with maximum severity , overall and by SOC and PT.

All ADEs will be listed, sorting by participant number, start date (placing missing and partial dates first) and end date, alphabetically by SOC, and then by PT within SOC. ADE duration in days will be calculated as (end date - start date + 1) and included in the data listings.

This document is confidential.

9.4. Device Deficiencies or Complaints

Device deficiency is defined as inadequacy of a medical device with respect to its identity, quality, durability, reliability, safety or performance, such as malfunctions, misuse or use errors, and inadequate labeling.

The number and percentage of participants with at least one device deficiency that could have led to an SADE, along with the numbers of these events, will be summarized by overall for the safety population. For participants with at least one device deficiency that could have led to a SADE, the reasons for these deficiencies will be summarized. Device deficiencies will also be listed.

9.5. Laboratory Evaluations

Screening for pregnancy (urine β -HCG) will be performed at the Screening and Treatment visits. The pregnancy test results will be listed.

9.6. [REDACTED]

[REDACTED]

[REDACTED]

[REDACTED]

[REDACTED]

This document is confidential.

10. Subgroup Analyses

All efficacy and key safety will be presented for the following subgroups as appropriate:

- Investigational site.
- Generation

The number and proportion of arms with correct identification of baseline vs. 12-week images of the upper arms by at least two out of three blinded, independent reviewers. Success will be defined as at least 75% correct identification of the pre-treatment images. The corresponding two-sided exact 95% CI of the proportion of arms with correct identification will be summarized by generation (1st and 2nd generation).

The number and proportion of thighs with correct identification of baseline vs. 12-week images of the inner thighs by at least two out of three blinded, independent reviewers and the corresponding two-sided exact 95% CI of the proportion of thighs with correct identification will be summarized by generation (1st and 2nd generation).

Participants who have reported 'Very satisfied' or 'Satisfied' on each of the CoolSculpting participant questionnaires (upper arms and inner thighs) for question #1 (overall satisfaction) will be categorized as 'Satisfied.' The numbers and proportions of 'Satisfied' at 12-weeks visit will be summarized and two-sided exact 95% CI of the proportions will be provided for arms and thighs, respectively summarized by generation (1st and 2nd generation).

Fat reduction using caliper measurements at 12-weeks compared to baseline for upper arms and inner thighs will be summarized descriptively using the change from baseline to week 12 for arms and thighs, respectively summarized by generation (1st and 2nd generation).

An overall summary of the number and percentage of participants reporting TEAEs, device-related TEAEs, procedure-related TEAEs, and SAEs, including the total number of device-related TEAEs, procedure-related TEAEs, and TESAEs, by site and by generation (1st and 2nd generation).

In addition, TEAEs by SOC and PT will be produced by site and by generation (1st and 2nd generation).

This document is confidential.

11. Interim Analyses

No interim analyses are planned for this study.

This document is confidential.

12. Changes from Analysis Planned in Protocol

[figure not shown]
1. 'Day 1' is used in this SAP for the study day where 'Day 0' is used in the protocol.
2. As per section 9.2 of the protocol, safety population was defined as 'The safety population will consist of all the treated participants with at least one safety evaluation after the treatment'; AT was defined as 'The AT population will consist of all treated participants regardless of weight change, etc.'. These two populations will consist same participants . Therefore, in the SAP, only one of them is defined as 'The safety population will consist of all the treated participants'.
3. Sample size is calculated based on number of arms. 'participants' is a typo in the protocol. So, the term 'participants' is replaced by 'arms' appropriately. Similarly, 'participants' is a typo in the protocol for primary and secondary effectiveness analyses. The term 'participants' is replaced by 'arms' or 'thighs', respectively. These are administrative changes.

This document is confidential.

[figure not shown]
13. Reference List

To be updated.

[figure not shown]
This document is confidential.

[figure not shown]
This document is confidential.

This document is confidential.

[figure not shown]
This document is confidential.

17. Index of Figures

No Figures

This document is confidential.

[figure not shown]

This document is confidential.

[figure not shown]
19. Table, Listing, and Figure Shells

This table, figure and listing shells will be provided as a separate document.

[figure not shown]
This document is confidential.

[figure not shown]
This document is confidential.

[figure not shown]
This document is confidential.

This document is confidential.

This document is confidential.

This document is confidential.

This document is confidential.
